15.1 RESEARCH PARTICIPANT REGISTRATION AND RANDOMIZATION PROCEDURES

15.2 Research Participant Registration

Confirm eligibility as defined in the section entitled Inclusion/Exclusion Criteria. Obtain informed consent, by following procedures defined in section entitled Informed Consent Procedures. During the registration process registering individuals will be required to complete a protocol specific Eligibility Checklist. The individual signing the Eligibility Checklist is confirming whether or not the participant is eligible to enroll in the study. Study staff are responsible for ensuring that all institutional requirements necessary to enroll a participant to the study have been completed. See related Clinical Research Policy and Procedure #401 (Protocol Participant Registration).

15.3 Randomization

NA

16.1 DATA MANAGEMENT ISSUES

A Research Study Assistant (RSA) will be assigned to the study. The responsibilities of the RSA include project compliance, data collection, abstraction and entry, data reporting, regulatory monitoring, problem resolution and prioritization, and coordinate the activities of the protocol study team.

The data collected for this study will be entered into CRDB. Source documentation will be available to support the computerized patient record. All research material from this study will be handled with the same confidentiality as patient's other medical data. Data collected will include toxicity data (CTCAE v 4.0 toxicity, IPSS, IIEF, and EPIC) as well as PSA and biopsy information.

16.2 Quality Assurance

An assigned RSA will work with the PI to ensure proper adherence to the protocol, eligibility verification, informed consent, and data accuracy.

Weekly registration reports will be generated to monitor patient accruals and completeness of registration data. Routine data quality reports will be generated to assess missing data and inconsistencies. Accrual rates and accuracy of evaluations and followup will be monitored periodically throughout the study period and potential problems will be brought to the attention of the study team for discussion and action.

Random sample data quality and protocol compliance audits will be conducted by the study team, at a minimum of twice per year or more frequently if indicated.

16.3 Data and Safety Monitoring

Eligibility of patients will be verified with the principal investigator. Only the designated investigators can obtain informed consent.

There are several different mechanisms by which clinical trials are monitored for data, safety and quality. There are institutional processes in place for quality assurance (e.g., protocol monitoring, compliance and data verification audits, therapeutic response, and staff education on clinical research QA) and departmental procedures for quality control, plus there are two institutional committees that are responsible for monitoring the activities of our clinical trials programs. The committees: *Data and Safety Monitoring Committee (DSMC)* for Phase I and II clinical trials, and the *Data and Safety Monitoring Board (DSMB)* for Phase III clinical trials, report to the Center's Research Council and Institutional Review Board (see section 16.2).

During the protocol development and review process, each protocol will be assessed for the level of risk and the degree of required monitoring. Every type of protocol (e.g., NIH sponsored, in-house sponsored, industrial sponsored, NCI cooperative group, etc.) is reviewed and monitoring procedures are established at the time of protocol activation.

The Data and Safety Monitoring (DSM) Plans at Memorial Sloan-Kettering Cancer Center were approved by the National Cancer Institute in September 2001. The plans address the

new policies set forth by the NCI in the document entitled "Policy of the National Cancer Institute for Data and Safety Monitoring of Clinical Trials" which can be found at: <http://cancertrials.nci.nih.gov/researchers/dsm/index.html>. The DSM Plans at MSKCC were established and are monitored by the Office of Clinical Research. The MSKCC Data and Safety Monitoring Plans can be found on the MSKCC Intranet at: <http://mskweb2.mskcc.org/irb/index.htm>.

17.1 PROTECTION OF HUMAN SUBJECTS

Patient Confidentiality: Patient/subject privacy and confidentiality will be maintained according to MSKCC guidelines and all data derived from this study will be kept in a secure database. All data and results will be anonymously reported with regard to individual subjects.

Voluntary nature of the study: Subjects will be made aware of the voluntary nature of the study as part of the informed consent process. They will be allowed to withdraw participation at any time without the risk of alteration in the quality of their medical care.

17.2 Privacy

MSKCC's Privacy Office may allow the use and disclosure of protected health information pursuant to a completed and signed Research Authorization form. The use and disclosure of protected health information will be limited to the individuals described in the Research Authorization form. A Research Authorization form must be completed by the Principal Investigator and approved by the IRB and Privacy Board (IRB/PB).

17.3 Serious Adverse Event (SAE) Reporting

An adverse event is considered serious if it results in ANY of the following outcomes:

- Death
- A life-threatening adverse event
- An adverse event that results in inpatient hospitalization or prolongation of existing hospitalization
- A persistent or significant incapacity or substantial disruption of the ability to conduct normal life functions
- A congenital anomaly/birth defect
- Important Medical Events (IME) that may not result in death, be life threatening, or require hospitalization may be considered serious when, based upon medical judgment, they may jeopardize the patient or participant and may require medical or surgical intervention to prevent one of the outcomes listed in this definition

Note: Hospital admission for a planned procedure/disease treatment is not considered an SAE.

SAE reporting is required as soon as the participant starts investigational treatment/intervention. SAE reporting is required for 30-days after the participant's last investigational treatment/intervention. Any event that occurs after the 30-day period that is unexpected and at least possibly related to protocol treatment must be reported.

Please note: Any SAE that occurs prior to the start of investigational treatment/intervention and is related to a screening test or procedure (i.e., a screening biopsy) must be reported.

All SAEs must be submitted in PIMS. If an SAE requires submission to the HRPP office per IRB SOP RR-408 „Reporting of Serious Adverse Events”, the SAE report must be submitted within 5 calendar days of the event. All other SAEs must be submitted within 30 calendar days of the event.

The report should contain the following information:

- The date the adverse event occurred
- The adverse event
- The grade of the event
- Relationship of the adverse event to the treatment(s)
- If the AE was expected
- Detailed text that includes the following
 - An explanation of how the AE was handled
 - A description of the participant's condition
 - Indication if the participant remains on the study
- If an amendment will need to be made to the protocol and/or consent form
- If the SAE is an Unanticipated Problem

For IND/IDE protocols: The SAE report should be completed as per above instructions. If appropriate, the report will be forwarded to the FDA by the IND Office

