LDR brachytherapy combined with conventional external beam radiotherapy for patients with intermediate risk prostate cancer addresses not only a need for dose escalation but also addresses concerns of dose coverage of extracapsular disease extension and is an accepted standard of care approach for intermediate risk disease (www.nccn.org). Long term outcomes using either LDR brachytherapy have been reported.^{12, 13, 15} We recently reported 7-year PSA relapse-free survival of 92% for patients with intermediate risk prostate cancer treated with prostate brachytherapy combined with 50.4Gy of external beam radiotherapy.¹⁴ With regards to toxicity, acute and late grade 3 or higher GU toxicity was noted in 2.3% and 3.1% respectively. Grade 2 late GU and GI toxicity were 21% and 4% respectively.

Although hypofractionated regimens for the definitive treatment of prostate cancer are considered part of a standard approach, the integration of a hypofractionated approach combined with brachytherapy has not yet been studied. To date, two ongoing studies are examining this in a Phase I setting (www.clinicaltrials.gov). The purpose of this study is to establish the toxicity associated with brachytherapy combined with hypofractionated radiation therapy.

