11.1 TOXICITIES/SIDE EFFECTS

The toxicities associated with radiation therapy to the prostate can be classified as either early (occurring within 90 days of treatment) or late (after 90 days). For the purpose of this study, the CTCAE v4.0 will be used as the primary endpoint to assess treatment-related toxicity. We expect that based on our prior studies^{14, 15}, 20% of patients of patients with have grade 2 or higher GU toxicity. The treatment will be considered to have significantly higher toxicity if ≥40% of patients in this study have ≥grade 2 at 12 months.

DEFINITIONS:

1. Adverse Event (AE)
 - a. An AE is defined by the GCP (Guide to Good Clinical Practice) as any undesirable experience occurring to a subject during a clinical trial, whether or not it is considered related to the investigational product(s).
2. Serious Adverse Event (SAE)
 - a. An SAE is an adverse experience that:
 - i. Is fatal or life-threatening
 - ii. Is disabling
 - iii. Results in hospitalization or prolongation of hospitalization
 - iv. Results in a congenital anomaly or occurrence of malignancy
 - v. Any urinary or rectal toxicity that is grade 3 or higher
3. Unexpected Adverse Event (UAE)
 - a. A UAE is an experience not previously reported (in nature, severity, or incidence) in the current Investigator's Brochure or general investigational plan.

Toxicities associated with radiation treatment include increased urinary frequency, urgency, weak stream, and nocturia. Other toxicities that may be related to radiation are fatigue, dysuria, hematuria, erectile dysfunction, urinary obstruction (due to edema or stricture), proctitis, bowel

injury or secondary cancers. Urinary, rectal, and erectile toxicities will be measured using IPSS, CTCAE v 4.0, and EPIC validated instruments (appendix).

The probability of severe (grade 3 or higher) urinary or rectal toxicity is expected to be $\leq 5\%$ which is currently observed rate of severe toxicity reported using standard combined brachytherapy and conventionally fractionated external beam radiation at MSKCC.¹⁴

To insure that unexpected significant toxicity is identified as early as possible with this treatment, we will observe the first 6 patients for a minimum of 3 months before enrolling any additional patients. If more than one patient has a grade 3 toxicity, we will wait 12 months before resuming accrual. If 4 or more patients of the first 6 patients have grade 3 or higher toxicity at 3 months we will terminate the study.

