12.1 CRITERIA FOR THERAPEUTIC RESPONSE/OUTCOME ASSESSMENT

The primary objective of this study is to assess toxicity associated with combined LDR brachytherapy and hypofractionated radiation therapy for intermediate risk prostate cancer at 12 months via CTCAE v4.0. Both acute and late toxicity associated with radiation therapy will be evaluated in a fashion similar to those used in prior studies of radiation therapy in prostate cancer patients. All grade 2 or higher toxicities will be evaluated and attributed to radiation therapy or not. Evaluation will be carried out prior to treatment to serve as a baseline. During each subsequent followup visit, patients will be asked to complete questionnaires (IPSS, IIEF, and EPIC) and asked about symptoms. The primary expected toxicities are genitourinary and gastrointestinal (rectal). Sexual function assessment is included but is not considered an SAE.

The following instruments will be used in the evaluation of toxicities:

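### Section 17.3 does not clearly require SAE reporting of anticipated late grade 3 or worse urinary and rectal events, which Section 11.1 defines as SAEs

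*Combined protocol and SAP*

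**What the plan says.** The protocol handles serious events in two places.

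- **Section 11.1, definitions.** Besides the usual seriousness criteria, the SAE list includes "Any urinary or rectal toxicity that is grade 3 or higher". No time limit is attached. The same section divides toxicity into "early (occurring within 90 days of treatment) or late (after 90 days").
- **Section 11.1, expectedness.** "A UAE is an experience not previously reported (in nature, severity, or incidence) in the current Investigator's Brochure or general investigational plan". The section names the known effects of treatment by type, without grades. They include obstruction from edema or stricture, hematuria, proctitis and bowel injury. It then gives a rate for severe events: "The probability of severe (grade 3 or higher) urinary or rectal toxicity is expected to be" 5% or less.
- **Section 12.1.** "The primary expected toxicities are genitourinary and gastrointestinal (rectal").
- **Section 3.0.** In the institution's series of brachytherapy plus 50.4 Gy, "acute and late grade 3 or higher GU toxicity was noted in 2.3% and 3.1% respectively".
- **Section 17.3.** The SAE list here has no grade 3 urinary or rectal criterion. "SAE reporting is required for 30-days after the participant's last investigational treatment/intervention". After that: "Any event that occurs after the 30-day period that is unexpected and at least possibly related to protocol treatment must be reported". A later sentence, with no time limit of its own, says that SAEs are to be entered in the institutional reporting system. The deadlines are 5 or 30 calendar days, counted from the event.
- **Evaluation of SAE, at the end of Section 11.** The investigators review the record and dosimetry and may continue, modify or discontinue the study before enrolling more patients.

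The primary objective (Section 2.1) is late urinary toxicity at about 12 months.

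**The concern.** The reporting window shuts before the toxicity that the trial was set up to measure can begin. Take a patient with a grade 3 stricture or grade 3 proctitis at month 8. Under 11.1 this is an SAE. Under 17.3 the general window has closed, and the remaining duty applies only if the event is unexpected. The protocol names both conditions as known effects and anticipates a small percentage of severe cases, so a reasonable investigator could classify the event as expected and file nothing.

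Accrual is planned over about 3 years, so early patients will reach their late period while others are still being enrolled. If the event is not filed promptly, a severe late event may reach those who can act on it later than it should.

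**Working it through.** **1. Does the window reach any late event?** Counting both periods from the last external beam fraction, general reporting ends at day 30 and late toxicity starts after day 90. The gap is 90 − 30 = 60 days. If the 90 days were instead counted from the implant, external beam starts about 28 days later, and five fractions every other weekday span about 9 to 11 days. The window then closes at about 28 + 9 + 30 = 67 to 28 + 11 + 30 = 69 days, still short of 90. On either count no late event falls inside it. Against 36 months of follow-up, 30 / 1,095 = 2.7%.

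**2. Is a late severe event caught by the rule for unexpected events?** The definition in 11.1 has three arms.

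| Arm | What the protocol already anticipates | Does an isolated late grade 3 event fall outside it? |
|---|---|---|
| Nature | Urinary, rectal and bowel effects listed in 11.1; called expected in 12.1 | Usually not |
| Severity | Grade 3 or higher toxicity anticipated in 11.1 and cited in 3.0 | Usually not at grade 3; arguable above that |
| Incidence | 5% or less (11.1); 3.1% late GU (3.0) | Not for the first one or two cases; yes if a clear excess appears |

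An anticipated event therefore has no clear duty attached. The incidence arm helps only once someone has counted enough cases to see an excess.

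**3. Do the two SAE lists agree?** No. A grade 3 urinary or rectal event without hospitalization, incapacity or important-medical-event status is an SAE in 11.1 but not in 17.3. The sections thus differ on what is an SAE as well as on how long SAEs are reported.

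**4. How many patients?** The plan gives no figure for this, so there is none to reproduce. Inputs: n = 45 (Section 1.0), p = 3.1% (Section 3.0), and the 5% ceiling (Section 11.1).

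- Expected number = n × p. At 3.1%: 45 × 0.031 = 1.4. At 5%: 45 × 0.05 = 2.25.
- P(at least one) = 1 − (1 − p)^n. At 3.1%: 1 − 0.969^45 = 0.758. At 5%: 1 − 0.95^45 = 0.901.
- P(at least two) at 5%, from the binomial distribution: 0.665.
- Sensitivity to n at 3.1%: with 44 patients (40 evaluable plus 4 replacements, Section 14.0), 1.36 expected and 0.750; with the 40 evaluable only, 1.24 and 0.716.

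The 5% figure covers urinary and rectal toxicity together and is not split into early and late, so it is an upper guide. The 3.1% covers GU only, comes from a different external beam schedule, and has no stated follow-up period.

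**5. Timing.** From month 6 the visits are 6 months apart. A 5-day or 30-day deadline counted from the event can already have passed when the site first hears of it at a visit.

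**The case against.** A reader might infer that late severe events are never reported. The text does not support that. Section 17.3 sets a minimum and bars nothing; events unexpected in nature, severity or incidence stay reportable; and its sentence on entering SAEs in the institutional system carries no time limit. That sentence could be read to cover late events. In context, though, it names the system and introduces the deadlines, and if it covered every SAE at any time, the 30-day limit and the test of unexpectedness would do no work. It leaves the duty unclear.

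A reader might also infer that the SAE review cannot operate for late events, or that it is the sole safeguard. Neither holds. The Evaluation of SAE paragraph follows 11.1's own definition and does not make a 17.3 report its trigger, so it can be read as covering the month-8 patient. Other safeguards exist:

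- CTCAE grading to month 36, and tabulation of all toxicities by type and grade;
- attribution of all grade 2 or higher toxicities (Section 12.1);
- the rule of 12 or more patients in 40 with grade 2 or higher GU toxicity at 1 year (Section 14.0);
- the pause and termination rules for the first six patients;
- study-team audits at least twice a year, and institutional monitoring.

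This stands, and it limits the point. None of these, however, requires prompt filing of an individual late severe event. The first-six rule looks at 3 months, and the Section 14.0 rule counts status at 1 year with no interim look stated.

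It is also fair that expectedness is judged case by case, that the hypofractionated combination had not been studied, and that the list of known effects carries no grades. Finally, Section 17.3 defers to an institutional procedure that is not in the documents and may add duties.

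**Conclusion.** The point holds as an inconsistency between Sections 11.1 and 17.3. A late urinary or rectal event of grade 3 or worse, of an anticipated type and frequency, is an SAE under one section, and the other does not clearly require it to be reported.

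The size is modest: most likely one or two patients (1.4 of 45 at 3.1%, with a 76% chance of at least one; 2.25 at the 5% ceiling). This assumes that the cited rate carries over to the new schedule and accrues within 36 months, and that investigators treat such events as expected. Fewer of these events would fall during accrual, because many patients would then have only part of their late follow-up.

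It is tempting to scale this up to a much higher toxicity rate. The documents give no such rate, and a rate well above 5% could itself make events unexpected by incidence and so reportable. The gap concerns prompt SAE reporting of a few individual events. It does not affect the primary endpoint data or the Section 14.0 decision rule.

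**What to change.** Reconcile the two sections by adding a paragraph to 17.3, for example:

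> Urinary or rectal toxicity of grade 3 or worse with at least a possible relation to study treatment is reported as an SAE, whether or not it is expected, from the start of treatment through the 36-month visit. Each such report is passed to the review described under Evaluation of SAE in Section 11. The reporting deadline runs from the date the site learns of the event.

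The SAE list in 17.3 should also carry the 11.1 criterion, so that both lists agree.

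The cost is a short amendment and a few extra SAE forms. CTCAE grades are already collected at each scheduled visit, so no new assessment is needed, and sample size, endpoint and decision rule stay as they are.

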18.1 INFORMED CONSENT PROCEDURES

Before protocol-specified procedures are carried out, consenting professionals will explain full details of the protocol and study procedures as well as the risks involved to participants prior to their inclusion in the study. Participants will also be informed that they are free to withdraw from the study at any time. All participants must sign an IRB/PB-approved consent form indicating their consent to participate. This consent form meets the requirements of the Code of Federal Regulations and the Institutional Review Board/Privacy Board of this Center. The consent form will include the following:

1. The nature and objectives, potential risks and benefits of the intended study.
2. The length of study and the likely follow-up required.
3. Alternatives to the proposed study. (This will include available standard and investigational therapies. In addition, patients will be offered an option of supportive care for therapeutic studies.)
4. The name of the investigator(s) responsible for the protocol.
5. The right of the participant to accept or refuse study interventions/interactions and to withdraw from participation at any time.

Before any protocol-specific procedures can be carried out, the consenting professional will fully explain the aspects of patient privacy concerning research specific information. In addition to signing the IRB Informed Consent, all patients must agree to the Research Authorization component of the informed consent form.

Each participant and consenting professional will sign the consent form. The participant must receive a copy of the signed informed consent form.

20.0 APPENDICES

- Appendix 1. NCI CTCAE version 4.0
- Appendix 2. International Prostate Symptom Score
- Appendix 3. International Index of Erectile function- Item 6
- Appendix 4. EPIC urinary, bowel and sexual domains
